# 7.4. Quality Control / Study Monitoring

In accordance with applicable regulations including GCP, study monitors will contact the ICs/ASAs prior to the start of the study to review with the IC/ASA staff the protocol, study requirements, and their responsibilities to satisfy regulatory, ethical, and VHC requirements.

When reviewing data collection procedures, the discussion will also include identification, agreement and documentation of data items for which the eCRF will serve as the source document. The study monitors will monitor the study and IC/ASA site activity to verify that the:

• Data are authentic, accurate, and complete.

- Safety and rights of participants are being protected.
- Study is conducted in accordance with the currently approved protocol and any other study agreements, GCP, and all applicable regulatory requirements.
- The IC/ASA staff and the head of the IC/ASA (where applicable) agrees to allow the monitor direct access to all relevant documents.

#### 8. CABENUVA AND CONCOMITANT THERAPY

The protocol only requires that the participant is initiating or continuing CABENUVA IM injections, dosed in accordance with the approved label [CABENUVA USPI, EDURANT USPI, VOCABRIA USPI]; no CABENUVA is provided by VHC. No dose reductions, modifications, or changes in the frequency of any components of CABENUVA will be allowed during the study beyond what is allowed within the approved CABENUVA label

The IC/ASA will refer to the most recent CABENUVA USPI, for the preparation and administration of CABENUVA [CABENUVA USPI].

# 8.1. Missed CANENUVA Injections

Adherence to the CABENUVA monthly or every 2-monthly injection dosing schedule is required. If a participant misses a scheduled injection visit, the referring HIV care provider must be notified. The HIV care provider is responsible for all medical management decision for participants after a missed dose, as described in the most recent USPI [CABENUVA USPI]. The IC/ASA staff should also notify the Medical Monitor of missed injections; however, the Medical Monitor is not responsible for decisions regarding medical management of missed injections.

Any changes in a participant's ART must be recorded in the eCRF. This includes oral dosing of VOCABRIA and EDURANT or other ART regimens to ensure anti-viral coverage during a planned or unplanned missed visit.

Participants receiving CABENUVA are anticipated to be at risk for development of virologic resistance if ART is interrupted. The time period during which participants are at risk for development of virologic resistance may be determined by the period between when drug levels fall below therapeutic values and when they fall below levels which exert selective pressure on HIV. This time period will vary by ART agent and is dependent upon effective concentration, inhibitory concentration, and half-life. Plasma concentrations of both drugs (cabotegravir, rilpivirine) may be measurable for more than one year following IM injections.

#### 8.2. Treatment of an Overdose

At the IC/ASA, an SOP will be developed for the management of treatment overdose following prescribing label information [CABENUVA USPI]. For this study, any dose of CABENUVA greater than listed in the prescribing information will be considered an overdose. All overdoses and any treatment for the overdosage should be recorded in the eCRF.

There is no known specific treatment for overdose with cabotegravir or rilpivirine. If overdose occurs, contact the PPD Medical Monitor immediately while monitoring the participant and apply standard supportive treatment as required, including monitoring of vital signs as well as observation of the clinical status of the patient, and record in the participants source documentation. Consider the prolonged exposure to cabotegravir and rilpivirine (components of CABENUVA) following injections when assessing treatment needs and recovery.

In the event of an overdose, the IC/ASA should:

- 1. Contact both the HIV care provider and the PPD Medical Monitor immediately.
- 2. Document the quantity of the excess dose as well as the duration of the overdosing in the eCRF.
- 3. Document any signs or symptoms the IC/ASA assess as related to the overdose in the eCRF

Decisions regarding dose interruptions or modifications will be made by the HIV care provider and may consult with the Medical Monitor based on the clinical evaluation of the participant.

## 8.3. Concomitant Therapy

HIV care providers and IC/ASA staff will monitor concomitant medications, referring to the most recent USPI [CABENUVA USPI], paying special attention to the contraindicated medications and medications with a potential for drug-drug interactions.

The IC/ASA will note all new concomitant medications and send to the HIV care provider. The IC/ASA should consult with the HIV care provider if any new contraindicated or concomitant medications with the potential for drug interactions are noted prior to administering CABENUVA. Contraindicated or concomitant medications with the potential for drug interactions must be recorded in the eCRF at each visit. The Medical Monitor should be contacted if there are any questions regarding concomitant or prior therapy.

# 9. DISCONTINUATION OF CABENUVA AND PARTICIPANT DISCONTINUATIONS

#### 9.1. Discontinuation of CABENUVA

It may be necessary for a participant to permanently discontinue CABENUVA. If CABENUVA is permanently discontinued, the participant will not remain in the study. See the SoA (Annex 1: Schedule of Activities) and the POT for data to be collected at the time of discontinuation of CABENUVA. All study and CABENUVA discontinuations will be captured in the eCRF.

A participant may have to discontinue CABENUVA due to moderate to severe (as clinically determined by the IC/ASA and/or HIV care provider) COVID-19 infection

(suspect, probable, or confirmed using the most recent version of the World Health Organization (WHO) case definition [WHO, 2020].

All study and CABENUVA discontinuations will be recorded.

# 9.2. Temporary Discontinuation

The referring HIV care providers will determine if a temporary discontinuation is appropriate for their PLWHIV, per the most recent USPI for CABENUVA [CABENUVA USPI]. The IC/ASA will capture temporary discontinuations and restart information in the eCRF. If the participant does not restart CABENUVA they will no longer be eligible to continue the study.

If the referring HIV care provider determines a temporary discontinuation of CABENUVA is appropriate, he/she is responsible for all medical management decisions regarding ART coverage during this time. The IC/ASA staff should also notify the Medical Monitor of temporary discontinuations; however, the Medical Monitor is not responsible for decisions regarding medical management of missed injections.

Any changes in a participant's ART must be recorded in the eCRF. This includes oral dosing of VOCABRIA and EDURANT or other ART regimens to ensure anti-viral coverage during a planned or unplanned missed visit.

## 9.3. Participant Discontinuation / Withdrawal from the Study

A participant may discontinue CABENUVA and withdraw from the study at any time at their own request or may be withdrawn at any time at the discretion of the IC/ASA or HIV care providers for safety (i.e., AE, SAE), behavioural, or compliance reasons (i.e., protocol deviation).

At the time of discontinuing from the study, if possible, an early discontinuation visit should be conducted, as shown in the SoA (Annex 1: Schedule of Activities) and the POT. The SoA includes the data to be collected at the time of study discontinuation and follow-up and for any further evaluations that need to be completed.

If the participant withdraws consent for disclosure of future information, the sponsor may retain and continue to use any data collected before such a withdrawal of consent.

# 9.4. Lost to Follow-up

A participant will be considered lost to follow-up if they fail to return for one or more scheduled visits and is unable to be contacted by the IC/ASA or the HIV care provider.

The following actions must be taken if a participant fails to return to the IC/ASA for a required study visit:

• The IC/ASA must immediately contact the HIV care provider if a participant has missed a visit.

- The IC/ASA must attempt to contact the participant and reschedule the missed visit as soon as possible and counsel the participant on the importance of maintaining the assigned visit schedule and ascertain whether or not the participant wishes to and/or should continue receiving monthly or every 2monthly injections at the IC/ASA.
- Before a participant is deemed lost to follow up, the IC/ASA and HIV care provider must make every effort to regain contact with the participant. These contact attempts should be documented in the participant's medical record.
- Should the participant continue to be unreachable, they will be considered to have withdrawn from the study with a primary reason of "Lost to Follow-up".

# 10. MANAGEMENT AND REPORTING OF ADVERSE EVENTS AND SAFETY ASSESSMENTS

Planned time points for all safety assessments are provided in the SoA, Annex 1 and in the POT. Definitions of AEs, SAEs and CV events can be found in Annex 3.

All AEs, SAEs and clinical laboratory abnormalities should be graded using the Division of AIDS (DAIDS) table for grading the severity of adult and pediatric adverse events [DAIDS, 2017].

## 10.1. Clinical safety laboratory assessments

All Baseline/Month 1 lab assessments should be drawn prior to the 1st study injections. If labs will be taken off-site from the IC/ASA, then the study participant should sign the ICF and receive a requisition for a blood draw at another location (i.e., Quest, Labcorp). Labs should be drawn 7-10 days prior to the Baseline/Month 1 visit. Confirmation that labs were drawn prior to the 1st study injections are mandatory, relevant labs should be added to the eCRF. If a potential participant has had labs drawn with 10 days of the Month 1/Baseline visit, and the HCP is willing to share that data, this data can then be used and added to the eCRF.

Local laboratory assessments for this study will be performed as per the blueprint and the POT at local laboratories. All laboratory reports will be shared with the HIV care provider. See the SRM for additional information.

- The HIV care provider will determine if any laboratory tests have values considered clinically significantly abnormal and will be responsible for the participant clinical management. The IC/ASA and HIV care provider will agree if follow-up labs are to be collected at the IC/ASA. The PPD Medical Monitor should be informed of abnormal laboratory tests considered clinically significant.
- The IC/ASA should document this review and record any HIV care provider determination of clinically significant changes occurring during the study as an AE/SAE. The PPD Medical Monitor should be informed. The laboratory reports must be filed with the source documents.
- If any laboratory test results require a change in participant management or are considered clinically significant by the HIV care provider, then the results must

be recorded in the eCRF as appropriate (e.g., abnormal lab results that are considered an SAE, CABENUVA related or required CABENUVA to be discontinued).

• If laboratory values from non-protocol specified laboratory tests performed at the HIV care provider's local laboratory require a change in participant management or are considered clinically significant by the provider then the results must be recorded in the eCRF as appropriate (e.g., abnormal lab results that are considered an SAE, CABENUVA-related AE, requires CABENUVA to be discontinued, or COVID-19 related).

It is expected that at a minimum, HIV-1 RNA and liver chemistries will be analyzed. Other lab assessments will be determined by the Expert Panel (e.g., absolute CD4 cell counts) and the POT between the HIV care provider and the IC/ASA.

- Liver chemistries should include:
  - Aspartate Aminotransferase (AST)/ Serum Glutamic-Oxaloacetic Transaminase (SGOT)
  - Alanine Aminotransferase (ALT)/ Serum Glutamic-Pyruvic Transaminase (SGPT)
  - Alkaline Phosphatase
  - o Total and direct Bilirubin

Additional tests may be performed at any time during the study as determined necessary by the HIV care provider.

# 10.2. Liver Chemistry Monitoring

The HIV care provider and the Medical Monitor must be contacted at onset of liver chemistry elevations to discuss participant safety. Liver event documents (i.e., "Liver Event eCRF" and updates, "Liver Imaging eCRF" and/or "Liver Biopsy eCRF", as applicable) should be completed as soon as possible. See the SRM for more information on liver events. Safety contact information can be found in Annex 4.

The decision whether to discontinue CABENUVA for abnormal liver tests should be made by HIV care provider. The POT between the IC/ASA and the HIV care provider will include the monitoring of liver chemistries and communications between the IC/ASA, HIV care provider, and the PPD Medical Monitor. The PPD Medical Monitor may request additional information regarding the results of and/or the monitoring of liver chemistries. Additional information can be found in Section 10.1 and in the SRM.

# 10.3. Adverse Events (AEs), Pregnancy Exposure and Incident Reporting

Clinical safety data will be collected as outlined in the eCRF. The complete definitions of adverse events (AE) or serious adverse events (SAEs) can be found in Annex 3. For AEs, only those that are considered related to CABENUVA, or that caused the

Protocol Amendment 06

participant to discontinue the study are required to be reported to PPD PVG (See Section 10.3.1). All AEs will be reported to the HIV care provider.

AEs will be reported by the participant (or, when appropriate, by a caregiver, surrogate, or the participant's legally authorized representative (LAR)) be collected and stored in the participants source documentation.

The IC/ASA staff and any qualified designees are responsible for detecting, documenting, and reporting events that meet the definition of an AE or SAE and remain responsible for following up AEs that are serious, considered related to CABENUVA or that cause the participant to discontinue CABENUVA from the time of the informed consent to participants withdrawal or completions of the study.

The method of recording, evaluating, and assessing causality of AEs and SAEs and the procedures for completing and transmitting SAE reports are provided in Section 10.3.10.

Please call the PPD safety hotline located in Annex 4 for AE/SAE assistance (i.e., is this event an SAE?) and for eCRF entry assistance.

#### 10.3.1. Specific Adverse Events to be Documented in this Study

Please refer to the most current USPIs for CABENUVA, VOCABRIA and EDURANT for additional safety information [CABENUVA USPI; EDURANT USPI, VOCABRIA USPI].

AEs and SAEs that are required to be recorded as defined in the eCRF include:

- AEs/Adverse drug reactions\* (ADRs) reported at the Baseline/Month 1 visit that are considered related to oral VOCABRIA or EDURANT or from the time of the last injections
- AEs/ADRs considered related to CABENUVA
- All AEs, whether considered related or not, that cause the participant to discontinue CABENUVA
- All SAEs whether related to CABENUVA or not
- All CV events listed in Annex 3
- COVID-19 related adverse events

Non serious AEs that are considered not related to CABENUVA or do not lead to withdrawal, should be documented in the source documents but will not be documented in the eCRF, as this information has been extensively collected in treatment clinical trials, no further information is needed to characterize these events.

\*An adverse drug reaction (ADR) is defined as a noxious and unintended response to a medication related to any doses where there is at least a reasonable possibility, or the relationship cannot be ruled out, that it is related to CABENUVA.

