# 4.3.1. Participants with HIV-1

PLWHIV are allowed in the study if they have been prescribed CABENUVA per the USPI [CABENUVA USPI] and meet all eligibility criteria (Section 4.2.1) at the Baseline/Month 1 visit. Participants meeting all eligibility criteria will sign the informed consent form at the IC/ASA and will enter into the study.

If a participant plans to miss the injections by more than 7 days, in consultation with the HIV care provider, oral VOCABRIA + EDURANT or other ART regimens should be taken daily to replace up to 2 consecutive planned missed monthly injection visits or every 2-month injection visit-doses. Dosing of oral bridging in the event of missed doses will be in accordance with the most recent CABENUVA prescribing information [CABENUVA USPI].

In consultation with the HIV care provider, participants may switch from monthly injections to an every-2-month continuation injection schedule, or from a 2-month continuation injection schedule to a monthly continuation dosing schedule. When switching dosing regimens, follow all instructions as outlined in the most current Prescribing Information [CABENUVA USPI]. The total duration of study participants is approximately 8 months from the time of enrolment, and receipt of the first study related administration of CABENUVA IM injections at the IC/ASA. A participant is considered to have completed the study if he/she has finished all Month 8 assessments.

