## 10.3.10. Reporting of AEs and Timelines

If the eCRF is down at the time of notification of these events, complete the applicable AE/SAE paper forms or other safety event eCRF and fax the completed forms to PPD PVG. All SAEs should be reported to PPD PVG immediately and under no circumstance should this exceed 24 hours. Please see Annex 4 for safety contact information the SRM for additional information on the follow-up of safety events.

AE or SAE information must include relationship to CABENUVA. Specific events requiring safety follow-up are:

- SAEs reported at the Baseline/Month 1 visit that are considered related to oral VOCABRIA or EDURANT or from the last injection
- All SAEs (Annex 3) whether related to CABENUVA or not

The non-serious AEs listed below will require reporting within 3 days to PPD PVG and will use the same automated safety alerts within the eCRF.

- AEs/Adverse drug reactions (ADRs) (Annex 3) reported at the Baseline/Month 1 visit that are considered related to oral VOCABRIA or EDURANT or from the last injection
- AEs/ADRs considered related to CABENUVA
  - Note: non-serious injection site reactions do not have to be reported to PPD
- All AEs, whether considered related or not, that cause the participant to discontinue CABENUVA (including ISRs)
- Cardiovascular AEs considered related to CABENUVA

Safety reporting timeline requirements for AE and SAE is summarized in Table 3.

Table 3 Reporting of Serious Adverse Events and Other Events

	Initia	l Reports	•	ation on a Previous port
Type of Event	Time Frame	Documents	Time Frame	Documents
All SAEs	24 hours	"SAE eCRF"	24 hours	Update "SAE eCRF"
Cardiovascular (CV) a or death event	Initial and follow- up reports to be completed when the CV event or death is reported b	'AE/SAE eCRF' and "CV events" and/or "death" eCRF	Initial and follow-up reports to be completed when the CV event or death is reported b	'Updated AE/SAE eCRF' and Update "CV events" and/or "death" eCRF
Pregnancy	24 hours	"Pregnancy Notification Form" and SAE (if required)	Within 24 hours of IC/ASA staff awareness of pregnancy outcome	"Pregnancy Follow-up Form" and SAE (if required)
Non serious ADRs c	3 days	eCRF	3 days	eCRF
AEs leading to withdrawal	3 days	eCRF	3 days	eCRF

- a. CV events are noted in Annex 3.
- b. Additional details and time frames for reporting supplementary information for cardiovascular and death events are provided in Section 10.3.12.

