# Annex 3.4 Recording and Follow-up of AEs and SAEs

# AE and SAE Recording

- When a CABENUVA-related AE, AE leading to withdrawal, or any SAE occurs, it is the responsibility of the HIV care provider to review all documentation (e.g., hospital progress notes, laboratory and diagnostics reports) related to the event.
- The IC/ASA will then record all relevant AE/SAE (VOCABRIA or EDURANT related AEs, CABENUVA-related AEs, AEs leading to withdrawal, all SAEs) information.
- If an event is not an AE per definition above, then it cannot be an SAE even if serious conditions are met (e.g., hospitalization for signs/symptoms of the disease under study, death due to progression of disease, etc.).
- It is **not** acceptable for the IC/ASA or HIV care provider to send photocopies of the participant's medical records to the Medical Monitor or the Sponsor in lieu of completion of the eCRF required forms.
- There may be instances when copies of medical records for certain cases are requested. In this case, all participant identifiers, with the exception of the participant number, will be redacted on the copies of the medical records before submission.
- The IC/ASA staff, working with the HIV care provider, will attempt to establish a diagnosis of the event based on signs, symptoms, and/or other clinical information. Whenever possible, the diagnosis (not the individual signs/symptoms) will be

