#### AE and SAE Recording

documented as the AE/SAE and recorded in the eCRF if it is a VOCABRIA-, EDURANT, or CABENUVA-related AE, an AE leading to withdrawal, or an SAE.

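### A non-serious AE attributed only to oral VOCABRIA or EDURANT during on-study bridging is kept out of the eCRF by Protocol 10.3.1 but sent into it by Annex 3.4

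*Protocol*

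**What the plan says.** Oral VOCABRIA and EDURANT can be taken in two periods. One is the lead-in before Baseline/Month 1. The other is on study: under Protocol 4.3.1, "oral VOCABRIA + EDURANT or other ART regimens should be taken daily to replace up to 2 consecutive planned missed monthly injection visits", and Sections 8.1 and 9.2 also provide for oral cover.

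Section 10.3.1 lists what goes into the eCRF. Its only entry for the oral drugs is AEs "reported at the Baseline/Month 1 visit that are considered related to oral VOCABRIA or EDURANT or from the time of the last injections". Its closing paragraph says: "Non serious AEs that are considered not related to CABENUVA or do not lead to withdrawal, should be documented in the source documents". The same sentence bars these events from the eCRF. Section 10.3.10 sets the same limit for 3-day reporting to pharmacovigilance: AEs "reported at the Baseline/Month 1 visit that are considered related to oral VOCABRIA or EDURANT or from the last injection".

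Annex 3.4 is worded differently. The site is to record all relevant information on "VOCABRIA or EDURANT related AEs, CABENUVA-related AEs, AEs leading to withdrawal, all SAEs". A later sentence, on preferring a diagnosis to individual symptoms, says the event is "recorded in the eCRF if it is a VOCABRIA-, EDURANT, or CABENUVA-related AE, an AE leading to withdrawal, or an SAE". Neither sentence is limited to a visit, a study period or serious events.

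Clinical SAP 4.7.1.1 follows 10.3.1. It treats non-serious, non-CABENUVA-related events as absent from the eCRF, and its only category specific to the oral drugs is Baseline AEs.

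**The concern.** The same tablets, producing the same kind of event, are handled differently according to when they were taken. An oral-drug-related AE from lead-in is collected. One from bridging is collected only if the site works from Annex 3.4 and not from 10.3.1. What reaches the database, and therefore the AE tables, could depend on which page a site follows. The reason that 10.3.1 gives for source-only handling, namely that earlier trials have already characterised such events, does not explain a difference between lead-in and bridging.

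The SAP does not settle it. A bridging event entered under Annex 3.4 would fall into the general AE tables. Whether it would also count as treatment-related is unclear: SAP 4.7.1.1.2 refers to study treatment without saying whether bridging tablets belong to it, and SAP 2.1 uses the name CABENUVA for an oral component, which blurs what being related to CABENUVA means.

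**Working it through.** The plan gives no figure to reproduce, so the check is textual: take one event and apply every recording rule to it.

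**Test event.** Onset during on-study bridging with VOCABRIA + EDURANT (say, Month 4); non-serious; attributed to the tablets and not to CABENUVA; no discontinuation; not a cardiovascular event listed in Annex 3; not COVID-19-related. The Protocol's abbreviation list defines CABENUVA as the two long-acting products, so attribution to the tablets alone is a distinct judgement.

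| Place | Rule that applies | Result |
|---|---|---|
| 10.3 | Pharmacovigilance reporting only if CABENUVA-related or causing study discontinuation | Not reported |
| 10.3.1, list | Oral-drug-related only if reported at Baseline/Month 1 | Not listed |
| 10.3.1, closing paragraph | Event "should be documented in the source documents but will not be documented in the eCRF" | Source only |
| 10.3.2 | Oral-drug-related AEs that begin in the lead-in | Silent on bridging |
| 10.3.7 | Non-serious, non-discontinuing, judged unrelated to CABENUVA | Not entered |
| 10.3.10 | Same Baseline/Month 1 limit | No 3-day report |
| Annex 3.1 | CABENUVA-related or discontinuing AEs only | Not recorded |
| Annex 3.4, recording bullet | VOCABRIA- or EDURANT-related AEs recorded | Recorded; eCRF not named |
| Annex 3.4, diagnosis sentence | VOCABRIA- or EDURANT-related AEs in the eCRF | **Entered** |
| Annex 3.4, intensity | eCRF grading names CABENUVA-related, discontinuing and serious events | Not graded |
| Annex 3.4, causality | Oral-drug eCRF entry tied to the time before enrolment | Silent on bridging |
| SAP 4.7.1.1 | Not in the eCRF, so not summarised | Not tabulated |

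The closing paragraph of 10.3.1 joins its two conditions with an or. That does not matter here, because the test event meets both.

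**Relaxing one condition at a time.** If the event is serious, causes CABENUVA discontinuation, is a listed cardiovascular event, is COVID-19-related, or is also judged CABENUVA-related, 10.3.1 already requires it in the eCRF and the conflict over eCRF entry disappears. If the bridging drug is another ART regimen, Annex 3.4 does not name it and there is no conflict.

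**Size.** The documents give neither a bridging rate nor an AE rate. As an illustration on assumed rates only: 120 participants × 10% to 20% bridging = 12 to 24; 12 × 10% = 1.2 and 24 × 20% = 4.8, so about 1 to 5 participants with a non-serious AE attributed to the oral drugs. At these rates that overstates the test class, since some would bridge with other ART and some events would also be judged CABENUVA-related.

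**The case against.** The strongest reply is that this is loose drafting and not two competing regimes. Nearly all the text points one way. Only one sentence of Annex 3.4 both covers on-study oral-drug-related AEs and names the eCRF; the other recording sentence speaks of relevant information and does not name it. Annex 3.1 and the intensity and causality paragraphs of Annex 3.4 lean towards 10.3.1. This stands as a description of the balance, but the one sentence is an explicit eCRF instruction with no time limit, and 10.3.1 and 10.3.7 exclude the same event.

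A second reply is that little is lost. Bridged participants will usually have been injected with the same two molecules, Section 8.1 says drug may remain measurable for over a year, and the ADR footnote in 10.3.1 covers relationships that cannot be excluded. Many bridging AEs could therefore be classed as CABENUVA-related and captured. This also stands, and it limits the point to a residue. It does not close the gap, because the causality wording in Annex 3.4 is stricter than the footnote.

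Third, restricting non-serious AE collection is a deliberate and explained choice, safety is a tertiary and unpowered objective, and source records and provider notification remain. All true, but the choice still has to be stated consistently.

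Finally, the eCRF completion guide and Study Reference Manual are not available here and may give sites one instruction. Divergent handling is therefore possible, not shown.

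**Conclusion.** The contradiction is real for the test event and for no wider class. It rests on reading CABENUVA as the injectable product, as the Protocol defines it, and on a provider attributing the event to the tablets alone. The number of such events cannot be derived from the documents; the 1 to 5 participants above depend wholly on assumed rates.

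Two stronger conclusions are tempting. A reader might infer that 10.3.1 loses every drug-related AE from bridging. It does not: serious, discontinuing, listed cardiovascular, COVID-19-related and CABENUVA-related events are all kept. A reader might also infer that the report will make bridging look free of drug-related non-serious AEs. The SAP plans no such display: Section 4.7.5 covers occurrences, duration, frequency and missed injections, and no listed table shows AEs by bridging period. What remains is a small inconsistency in safety-recording instructions that is cheap to remove and worth removing.

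**What to change.** State one recording rule for AEs related to oral VOCABRIA or EDURANT that expressly covers both lead-in and on-study bridging, and apply it in Protocol 10.3, 10.3.1 (first bullet and source-only paragraph), 10.3.2, 10.3.7, 10.3.10, Annex 3.1 and Annex 3.4, and in clinical SAP 4.7.1.1. Changing only 10.3.1 and 10.3.10 would leave the remaining sections in conflict. In the SAP, count such on-study events in the treatment-related AE tables and flag those with onset during a bridging period.

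The cost is aligned wording in these sections, a few extra AE entries and slightly more analysis work. No visits are added: AEs are already reviewed throughout follow-up and held in source documents.
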